### 7.3.13 Month 12 ( $\pm$ 7 Days) / Early Termination for the 12-month Double-blind ALN-controlled Study Period

#### For all subjects

- PRO/ClinRO questionnaires: OPAQ SV, EQ-5D-5L, LAD, and BPI worst pain (should preferably be completed before any other study procedures are performed)
- Physical examination
- Vital signs: blood pressure, temperature, and pulse
- Height and weight
- Blood sample for serum chemistry, hematology, and anti-romosozumab antibody
- Lateral spine x-rays (lumbar and thoracic), submitted to the central imaging vendor as soon as possible following the visit
- DXA scans of lumbar spine and proximal femur, submitted to the central imaging vendor as soon as possible following the visit
- Nonvertebral and suspected clinical vertebral fracture reporting
- Adverse event and concomitant medications data collection
- Unused oral IP (ALN/placebo) collection (blinded)
- ALN dispensation (open-label, 6-month supply)

#### For subjects participating in the Imaging and PK/BTM/Biomarker sub-study

- Blood sample for romosozumab levels
- Fasting blood sample for P1NP, sCTX, BSAP, and OC
- Blood sample for sclerostin and iPTH
- Blood sample (serum and plasma) for novel biomarker development
- For subjects also participating in the imaging components: QCT of the spine, submitted to the central imaging vendor as soon as possible following the visit

Note: If a subject terminates early from the study between the Day 1 and Month 12 visits, the Month 12 procedures except open-label ALN dispensation are to be completed at that time. DXA scans and lateral spine x-rays should be performed if at least 6 weeks have elapsed since the previous one.

### 7.3.14 Month 15 ( $\pm$ 14 Days) for Sub-study Subjects Only

#### For subjects participating in the Imaging and PK/BTM/Biomarker sub-study

- Nonvertebral and suspected clinical vertebral fracture reporting
- Adverse event and concomitant medications data collection
- Fasting blood sample for P1NP and sCTX
- Blood sample for sclerostin and iPTH
- Blood sample (serum and plasma) for novel biomarker development

### 7.3.15 Month 18 ( $\pm$ 14 Days)

#### For all subjects

- PRO/ClinRO questionnaires: OPAQ SV, EQ-5D-5L, LAD, and BPI worst pain (should preferably be completed before any other study procedures are performed)
- Vital signs: blood pressure, temperature, and pulse
- Height and weight
- Blood sample for serum chemistry and hematology
- Blood sample for anti-romosozumab antibody
- Nonvertebral and suspected clinical vertebral fracture reporting
- Adverse event and concomitant medications data collection
- ALN dispensation (open-label, 6-month supply)
- Unused ALN collection (open-label)

#### For subjects participating in the Imaging and PK/BTM/Biomarker sub-study

- Fasting blood sample for P1NP and sCTX
- Blood sample for sclerostin and iPTH
- Blood sample (serum and plasma) for novel biomarker development
- For subjects participating in the imaging components: DXA scans of lumbar spine and proximal femur, submitted to the central imaging vendor as soon as possible following the visit

### 7.3.16 Month 24 ( $\pm$ 14 Days) / Early Termination for Month 12 to Month 24 of the Primary Analysis Period

#### For all subjects

- PRO/ClinRO questionnaires: OPAQ SV, EQ-5D-5L, LAD, and BPI worst pain (should preferably be completed before any other study procedures are performed)
- Physical examination
- Vital signs: blood pressure, temperature, and pulse
- Height and weight
- Blood sample for serum chemistry, hematology, and anti-romosozumab antibody
- Lateral spine x-rays (lumbar and thoracic), submitted to the central imaging vendor as soon as possible following the visit
- DXA scans of lumbar spine and proximal femur, submitted to the central imaging vendor as soon as possible following the visit
- Nonvertebral and suspected clinical vertebral fracture reporting
- Adverse event and concomitant medications data collection
- ALN dispensation (open-label, 6-month supply)
- Unused ALN collection (open-label)

For subjects participating in the Imaging and PK/BTM/Biomarker sub-study

- Fasting blood sample for P1NP and sCTX
- Blood sample for sclerostin and iPTH
- Blood sample (serum and plasma) for novel biomarker development
- For subjects participating in the imaging components: QCT of the spine, submitted to the central imaging vendor as soon as possible following the visit

Note: If a subject terminates early from the study between the Month 12 and Month 24 visits, Month 24 procedures except ALN dispensation are to be completed at that time. DXA scans and lateral spine x-rays should be performed if at least 6 weeks have elapsed since the previous one.

**7.3.17 Month 30 ( $\pm$  14 Days)**

For all subjects

- PRO/ClinRO questionnaires: OPAQ SV, EQ-5D-5L, LAD, and BPI worst pain (should preferably be completed before any other study procedures are performed) (primary analysis period only)
- Vital signs: blood pressure, temperature, and pulse
- Height and weight
- Blood sample for serum chemistry and hematology (to be processed and sent to the central laboratory during the primary analysis period; to be analyzed at local laboratories following the primary analysis period, See [Section 7.8.1](#))
- Nonvertebral fracture reporting
- Suspected clinical vertebral fracture reporting (primary analysis period only)
- Adverse event and concomitant medications data collection
- ALN dispensation (open-label, 6-month supply)
- Unused ALN collection (open-label)

**7.3.18 Month 36 and Subsequent Clinic Visits ( $\pm$  14 Days) to End of Primary Analysis Period**

For all subjects, at Month 36 and every 6 months thereafter until the end of the primary analysis period

- PRO/ClinRO questionnaires: OPAQ SV, EQ-5D-5L, LAD, and BPI worst pain (should preferably be completed before any other study procedures are performed) (primary analysis period only)
- Physical examination
- Vital signs: blood pressure, temperature, and pulse
- Height and weight
- Blood sample for serum chemistry and hematology (to be processed and sent to the central laboratory during the primary analysis period)
- Nonvertebral fracture reporting

- Suspected clinical vertebral fracture reporting (primary analysis period only)
- Adverse event and concomitant medications data collection
- ALN dispensation (open-label, 6-month supply)
- Unused ALN collection (open-label)

For all subjects, at Month 36 and every 12 months thereafter **until the end of the primary analysis period**

- Lateral spine x-rays (lumbar and thoracic), submitted to the central imaging vendor as soon as possible following the visit (primary analysis period only)
- DXA scans of lumbar spine and proximal femur, submitted to the central imaging vendor as soon as possible following the visit (primary analysis period only)

For subjects participating in the Imaging and PK/BTM/Biomarker sub-study, at Month 36 or until end of the primary analysis period, **whichever comes first**

- Fasting blood sample for P1NP and sCTX
- Blood sample for sclerostin and iPTH
- Blood sample (serum and plasma) for novel biomarker development

Note: If a subject terminates early from the study between the Month 24 and the end of the primary analysis period, the Month 36 procedures are to be completed at that time (except ALN dispensation). DXA scans and lateral spine x-rays should be performed if at least 6 weeks have elapsed since the previous one.

### **7.3.19 Clinical Visits After the Primary Analysis Period to End of Study**

**For all subjects, at every 6-month clinic visit thereafter**

- **Physical examination**
- **Vital signs: blood pressure, temperature, and pulse**
- **Height and weight**
- **Blood sample for serum chemistry and hematology (to be analyzed at local laboratories following the primary analysis period, chloride, bicarbonate, and calculated adjusted calcium assessments are optional after primary analysis. (See [Section 7.8.1](#))**
- **Nonvertebral fracture reporting**
- **Adverse event and concomitant medications data collection**
- **ALN dispensation (open-label, 6-month supply)**
- **Unused ALN collection (open-label)**

### **7.3.20 Monthly Telephone Contacts in Between Clinic Visits ( $\pm$ 7 Days) Until end of Study**

For all subjects

- Nonvertebral fracture reporting
- Adverse event and concomitant medications data collection

Procedure for reporting of nonvertebral fractures during monthly telephone contacts:

When nonvertebral fractures are reported during the monthly telephone contacts, the same process as for nonvertebral fracture reporting at clinic visits should be followed. No unscheduled follow-up clinic visit or further unscheduled assessments will be required. The event should be recorded on the respective eCRF and copies of radiographs or other diagnostic images and/or a copy of the radiology report, surgical report, or discharge summary should be obtained, included in the subject's study records and submitted to the central imaging vendor.

For the primary analysis period only: Procedure for reporting of an adverse event of back pain during monthly telephone contacts:

When back pain is reported during the monthly telephone contacts, the back pain (but not a vertebral fracture) will be recorded as an adverse event, and the subject will be asked to complete an unscheduled follow-up clinic visit as soon as possible but no later than 21 days after reporting of the back pain (refer to Section 7.3.21).

Refer to [Section 7.11.1](#) and [Section 7.11.2](#) for general information about nonvertebral and suspected clinical vertebral fracture reporting procedures.

### **7.3.21 Unscheduled Follow-up Clinic Visit (+ 21 Days After Monthly Phone Contact) (Primary Analysis Period Only)**

For subjects who have reported back pain as an adverse event during the monthly telephone contact:

- Suspected clinical vertebral fracture reporting

For subjects for whom the previously reported back pain is considered to be possibly due to a new or worsening vertebral fracture:

- Lateral spine x-rays (lumbar and thoracic), submitted to the central imaging vendor as soon as possible following the visit

Procedure for reporting of suspected clinical vertebral fractures during the unscheduled follow-up clinic visit:

Unscheduled follow-up clinic visits will only be completed if back pain is reported during the monthly phone contact. The follow-up clinic visit has to be completed as soon as possible after the phone call but no later than 21 days after reporting of the back pain.

At the unscheduled follow-up clinic visit, the investigator will evaluate if the back pain is possibly due to a new or worsening vertebral fracture, and the respective eCRF will be completed. If the investigator considers the back pain to be possibly due to a new or worsening vertebral fracture, a confirmatory lateral spine x-ray will be taken and submitted to the central imaging vendor as soon as possible following the visit.

**7.3.22 Telephone Contact at “End of Primary Analysis Period” (–14 Days to end of Primary Analysis Period)**

For all subjects

- Nonvertebral fracture reporting
- Adverse event and concomitant medications data collection
- ALN compliance reporting (open-label)

The procedure for reporting of nonvertebral fractures during the end of primary analysis period telephone contact is the same as for the monthly telephone contacts (refer to [Section 7.3.19](#)).

If back pain is reported during the end of primary analysis period telephone contact, the back pain (but not a vertebral fracture) will be recorded as an adverse event. The subject will not be asked to complete an unscheduled follow-up clinic visit.

**Note: If all the data required for an end of primary analysis telephone call has already been obtained during the 14 days prior to the end of the primary analysis period, no additional end of primary analysis period telephone call will be necessary.**

**7.3.23 End of Study Telephone Contact (–14 to + 7 Days)**

For all subjects

- Adverse event and concomitant medications data collection
- ALN compliance reporting (open-label)

**Note: The end of study telephone contact will not be necessary for subjects who have had a clinic visit or have been contacted during this timeframe if all data required for the end of study telephone contact have been collected. The subjects, however, may be contacted after this time for additional safety information, follow-up, or possible follow on study opportunities.**

If a nonvertebral fracture is reported during the end of study telephone contact, the fracture will be recorded as an adverse event. Copies of the radiographs, diagnostic images and/or radiology report, surgical report, clinical notes, or discharge summary need not be obtained.

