## **10.5.2 Analysis of Key Study Endpoints**

### **10.5.2.1 Efficacy Endpoints**

#### **Clinical Fractures**

Clinical fractures include nonvertebral fractures and clinical vertebral fracture (with  $\geq 1$  grade increase from the previous grade in any vertebra from T4 to L4) that are associated with signs and/or symptoms indicative of a fracture. All nonvertebral fractures confirmed by the central imaging vendor, except those of the skull, face, fingers, and toes, which are typically not associated with osteoporosis, will be included in analyses. However, fractures associated with high trauma severity or pathologic fractures will be excluded.

Subject incidence of clinical fracture at pre-specified time points will be estimated for each treatment group using Kaplan-Meier method. The treatment effect on clinical fractures will be assessed based on the hazard ratio, corresponding 95% confidence interval, and the p-value of the score test from a Cox proportional hazards model controlling for stratification factor age ( $< 75$  or  $\geq 75$  years), presence or absence of severe vertebral fracture at baseline, and baseline total hip BMD T-score. For subjects who have one or more clinical fractures from randomization to a pre-specified time point, the first event is used to define time to first clinical fracture. Subjects who do not have clinical fractures from randomization to a pre-specified time point will be censored at the date of last evaluation for clinical fractures prior to the pre-specified time point. Graphical representations of the clinical fracture incidence over time will also be displayed using Kaplan-Meier curves.

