### **Time to First Event in Overall Study Period**

The time to event in the overall study period is defined similarly as for time to first event in double-blind period. Subjects who did not have any event will be censored on the date of last evaluation for the event, which is the End of Study Date recorded on the End of Study eCRF.

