## **6.4 Fracture-related Study Endpoints**

All the fracture related efficacy endpoints are based on the results from the central imaging vendor analysis transferred to the Amgen database.

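### If the study runs to 440 events, a nonvertebral fracture first reported at the end-of-study call need not be confirmed, and the woman is ordinarily analysed as event-free past it

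*Protocol*

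**What the plan says.** **The end-of-study call.** Protocol 7.3.23 gives this call two tasks: adverse events with concomitant medication, and ALN compliance. Nonvertebral fracture reporting is not listed. If a fracture comes up anyway, "If a nonvertebral fracture is reported during the end of study telephone contact, the fracture will be recorded as an adverse event", and "Copies of the radiographs, diagnostic images and/or radiology report, surgical report, clinical notes, or discharge summary need not be obtained". A clinic visit or other contact in the −14 to +7 day window can replace the call if it collected the same data.

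**Other contacts.** Protocol 7.3.20, which covers monthly calls until end of study, says "When nonvertebral fractures are reported during the monthly telephone contacts, the same process as for nonvertebral fracture reporting at clinic visits should be followed". Protocol 7.11.2 has every on-study nonvertebral fracture recorded and its images or reports submitted to the central imaging vendor. A woman who leaves early after the primary analysis period gets the end-of-primary-period call (Appendix A, note d), and that call includes nonvertebral fracture reporting (7.3.22).

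**What counts.** Protocol 10.5.2.1 includes "All nonvertebral fractures confirmed by the central imaging vendor, except those of the skull, face, fingers, and toes". SAP 6.4 says "All the fracture related efficacy endpoints are based on the results from the central imaging vendor analysis transferred to the Amgen database". SAP 6.4.3 needs an image or a report, and SAP 6.3 takes the event date from that document.

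**When follow-up ends.** SAP 6.1.2 and 6.1.3 end the overall study period on the date at least 440 subjects have a confirmed nonvertebral fracture. SAP 6.3 instead censors event-free women on "the date of last evaluation for the event, which is the End of Study Date recorded on the End of Study eCRF". Appendix A, footnote 9, places the end-of-study calls after the 440 are confirmed.

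**The concern.** Because the call follows the 440th confirmation, the time since a woman's last ordinary contact can include days before the cut-off. A fracture in those days belongs to the analysis period. If she first mentions it at the end-of-study call, the stated rule makes it an adverse event without documents, and nothing in the SAP turns an adverse-event fracture into an endpoint event. She then contributes event-free time up to a date described as the last evaluation for an event that this call does not evaluate.

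Whether the same fracture counts therefore depends on which contact picks it up. A monthly call or clinic visit in the same window would send it for confirmation. Women who leave early after the primary analysis are, at exit, ascertained more fully than completers whose last contact is the end-of-study call.

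Nonvertebral fracture is the last test in the alpha-controlled sequence. Hip and major nonvertebral fracture at the final analysis rest on the same ascertainment. The SAP describes no reconciliation of adverse-event fractures with the endpoint and no sensitivity analysis for this.

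**Working it through.** **1. The plan's own figures reproduce.**
- Spending at information fraction 0.8: 0.025 × ln(1 + (e − 1) × 0.8) = 0.0216. Solving the two-look boundary with correlation √0.8 gives a final one-sided level of 0.0119. Both match Protocol 10.2.
- Schoenfeld's formula for hazard ratio 0.70, 90% power, two-sided 0.05 gives 331 events; the plan has 330.
- A simulation of 2,000 trials gives joint power at the primary or final analysis of 84.2% (ALN rate 4.0% per year) or 83.4% (5.5% × 0.75 = 4.125%). The plan says approximately 84%. The BMD steps, each with over 99% power, were taken as passed.

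**2. Women at risk at the cut-off.** Inputs from Protocol 10.2: 2,000 per arm, 34-month enrolment, ALN rate 4% per year, 27% reduction (0.040 × 0.73 = 0.0292), dropout 10% in year 1 and 8% per year thereafter. Uniform accrual is an assumption, since only the 34-month total is given. The 440th event falls at about 5.5 years with about 1,181 + 1,234 = 2,415 women still at risk of a first nonvertebral fracture. With the 4.125% rate the figure is 2,451.

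**3. Fractures in the gap.** Expected first fractures per year are 1,181 × 0.040 + 1,234 × 0.0292 = 47.2 + 36.0, about 83.3, or 6.9 per month. Suppose every woman has the same gap since her last ordinary contact:

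| Gap | 83.3 × days/365.25 | Simulated, 4.0% | Simulated, 4.125% |
|---|---|---|---|
| 14 days | 3.2 | 4.2 | 4.4 |
| 30 days | 6.8 | 7.8 | 8.3 |
| 37 days | 8.4 | 9.4 | 10.0 |

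The simulated counts run about one higher because the cut-off is set at the 440th event, which then lies inside every gap. Thirty-seven days is one month plus the 7-day tolerance. So 4 to 10 fractures, or 1% to 2% of 440, is an upper range. If contacts are spread evenly over the month (an assumption), the mean gap is half a month: 6.9 × 0.5, about 3.5 fractures, or 0.8% of 440.

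**4. Power.** Power = Φ(½√d × |ln 0.73| − 2.26), where 2.26 is the normal quantile for one-sided 0.0119.
- d = 440: 10.49 × 0.3147 − 2.26 = 1.04, giving 0.851
- d = 445: 0.855
- d = 450: 0.859

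Five to ten extra events therefore add less than 1 percentage point.

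**5. Limit of the simulation.** Under uniform accrual it gives a median of 433 to 444 clinical fractures at the primary analysis (the plan has 396) and 81% joint power there (the plan has about 78%). The plan's accrual pattern is not stated. The gap counts depend mainly on the number at risk and are little affected.

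**The case against.** The strongest reply is that the effect is tiny and conditional. If nonvertebral superiority is shown at the primary analysis and the study stops, later data are descriptive only (Protocol 10.5.1), and the plan puts joint power at that look at about 78%. Only a woman with no earlier confirmed nonvertebral fracture is affected. A fracture dated after the cut-off is rightly excluded. Some women will have had an ordinary contact near the cut-off, and some reported fractures would fail the site, trauma or pathology exclusions in SAP 6.4.3. The rule is the same in both arms, and women and sites remain blinded to initial assignment. All of this stands, and it limits the size.

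Three stronger readings are tempting, but the documents do not support them:
- **That such a fracture can never reach the vendor.** Protocol 7.3.23 waives the documents; it does not forbid sending them, and 7.11.2 still states the general rule. The defect is a conflict between sections, with the waiver as the specific instruction.
- **That the event-driven test runs short of information.** The call follows confirmation of 440 subjects, so the planned events are already in hand. What is lost is surplus events.
- **That back pain at the end-of-primary-period call has the same flaw.** There, "The subject will not be asked to complete an unscheduled follow-up clinic visit", unlike after a monthly call. But a follow-up visit may come up to 21 days later (7.3.21) and SAP 6.3 dates a fracture by the confirming film. That film may fall after the period closes and would not count. A lost in-period event is not established.

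**Conclusion.** The point holds as a small, clear inconsistency. Protocol 7.3.23 conflicts with 7.11.2 and 7.3.20 on how an on-study nonvertebral fracture is handled. The censoring date in SAP 6.3 conflicts with the end of the overall study period in SAP 6.1.2 and 6.1.3. Followed as written, the two together would ordinarily drop known in-period fractures and keep the time after them as event-free.

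The size is at most about 4 to 10 first fractures if the study continues to the final analysis, and probably about 4 or fewer with staggered monthly contacts. No directional bias is shown. These figures rest on the plan's fracture and dropout rates, uniform accrual and the assumed gap lengths. The case for acting is that the correction is cheap and removes two contradictions, not that the result is at risk.

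**What to change.** 1. **Protocol 7.3.23 and Appendix A:** add nonvertebral fracture reporting to the end-of-study contact. For any fracture dated on or before the End of Final Analysis Period Date, replace the waiver with the documentation and central confirmation required by 7.3.20 and 7.11.2.
2. **SAP 6.3, overall study period:** censor event-free women at the earlier of the End of Final Analysis Period Date and their last contact that included nonvertebral fracture ascertainment. This brings the censoring rule into line with SAP 6.1.2 and 6.1.3.

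The cost is one protocol sentence, one mark in Appendix A, one SAP line, documents and central reading for about ten fractures or fewer, and a slightly later database lock.
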